10.2 MANAGEMENT OF IMMUNE-RELATED ADVERSE EVENTS

Management of immune-related adverse event toxicities associated with anti-PD-1 mAbs are presented below. **BI 754091 and BI 754111 should be permanently discontinued for Grade 3-4 pneumonitis, Grade 3-4 adrenal insufficiency, Grade 4 diabetes mellitus, any grade encephalitis, Grade 4 hypophysitis, Grade 4 rash, Grade 3-4 or recurrent colitis of any grade, any recurrent Grade 3-4 AE, transaminase increased >5 times ULN or total bilirubin >3 times ULN (unless unequivocally attributably to another cause), inability to taper steroids to 10 mg or less prednisone or equivalent within 12 weeks, or persistent Grade 2-3 AEs that do not recover to Grade 1 or less within 12 weeks.**

- Pneumonitis:
 - For Grade 2 events, treat with systemic corticosteroids. When symptoms improve to Grade 1 or less, steroid taper should be started and continued over no less than 28 days.
 - Add prophylactic antibiotics for opportunistic infections in the case of prolonged steroid administration.
 - For Grade 3-4 events immediately treat with i.v. steroids. Administer additional anti-inflammatory measures, as needed.
 - BI 754091 and BI 754111 should be permanently discontinued for Grade 3-4 pneumonitis, inability to taper steroids to 10 mg or less prednisone or equivalent within 12 weeks, or persistent Grade 2 AEs that do not recover to Grade 1 or less within 12 weeks.
- Diarrhoea/Colitis:

Subjects should be carefully monitored for signs and symptoms of enterocolitis (such as diarrhoea, abdominal pain, blood or mucus in stool, with or without fever) and of bowel perforation (such as peritoneal signs and ileus).

 - All subjects who experience diarrhoea/colitis should be advised to drink liberal quantities of clear fluids. If sufficient oral fluid intake is not feasible, fluid and electrolytes should be substituted via i.v. infusion. For Grade 2 or higher diarrhoea, consider GI consultation and endoscopy to confirm or rule out colitis.
 - For Grade 2 diarrhoea/colitis that persists greater than 3 days, administer oral corticosteroids.
 - For Grade 3 or 4 diarrhoea that persists >1 week, treat with i.v. steroids followed by high-dose oral steroids.
 - For Grade 3 or 4 colitis, or recurrent colitis of any grade, permanently discontinue BI 754091 and BI 754111, and immediately treat with i.v. steroids followed by high-dose oral steroids.
 - When symptoms improve to Grade 1 or less, steroid taper should be started and continued over no less than 28 days.
 - BI 754091 and BI 754111 should be permanently discontinued for Grade 3-4 or recurrent colitis of any grade, inability to taper steroids to 10 mg or less prednisone or equivalent within 12 weeks, or persistent Grade 2-3 AEs that do not recover to Grade 1 or less within 12 weeks.
- Type 1 diabetes mellitus (if new onset, including diabetic ketoacidosis) Grade 3, or \geq Grade 3 hyperglycaemia, if associated with ketosis (ketonuria) or metabolic acidosis
 - For Type 1 diabetes mellitus Grade 3-4 or Grade 3-4 hyperglycaemia

Proprietary confidential information © 2021 Boehringer Ingelheim International GmbH or one or more of its affiliated companies

- Insulin replacement therapy is recommended for Type I diabetes mellitus and for Grade 3-4 hyperglycaemia associated with metabolic acidosis or ketonuria.
- Evaluate subjects with serum glucose and a metabolic panel, urine ketones, glycosylated haemoglobin, and C-peptide.
- BI 754091 and BI 754111 should be permanently discontinued for Grade 4 diabetes mellitus, any recurrent Grade 3 AE or persistent Grade 2-3 AE that does not recover to Grade 1 or less within 12 weeks.
- Hypophysitis:
 - For Grade 2 events, treat with corticosteroids. When symptoms improve to Grade 1 or less, steroid taper should be started and continued over no less than 28 days. Replacement of appropriate hormones may be required as the steroid dose is tapered.
 - For Grade 3 events, treat with an initial dose of i.v. corticosteroids followed by oral corticosteroids. When symptoms improve to Grade 1 or less, steroid taper should be started and continued over no less than 28 days. Replacement of appropriate hormones may be required as the steroid dose is tapered.
 - For Grade 4 events, permanently discontinue BI 754091 and BI 754111, and treat with an initial dose of i.v. corticosteroids followed by oral corticosteroids. When symptoms improve to Grade 1 or less, steroid taper should be started and continued over no less than 28 days. Replacement of appropriate hormones may be required as the steroid dose is tapered.
 - BI 754091 and BI 754111 should be permanently discontinued for Grade 4 hypophysitis, any recurrent Grade 3 AE, inability to taper steroids to 10 mg or less prednisone or equivalent within 12 weeks, or persistent Grade 2-3 AEs that do not recover to Grade 1 or less within 12 weeks.
- Hyperthyroidism or Hypothyroidism:

Thyroid disorders can occur at any time during treatment. Monitor subjects for changes in thyroid function (at the start of treatment, periodically during treatment, and as indicated based on clinical evaluation) and for clinical signs and symptoms of thyroid disorders.

 - For Grade 2 hyperthyroidism events (and Grade 3-4 hypothyroidism):
 - In hyperthyroidism, nonselective beta-blockers (e.g., propranolol) are suggested as initial therapy.
 - In hypothyroidism, thyroid hormone replacement therapy, with levothyroxine or liothyronine, is indicated per standard of care.
 - For Grade 3-4 hyperthyroidism
 - Treat with an initial dose of i.v. corticosteroid followed by oral corticosteroids. When symptoms improve to Grade 1 or less, steroid taper should be started and continued over no less than 28 days. Replacement of appropriate hormones may be required as the steroid dose is tapered.
 - BI 754091 and BI 754111 should be permanently discontinued for any recurrent Grade 3-4 AE, inability to taper steroids to 10 mg or less prednisone or equivalent within 12 weeks, or persistent Grade 2-3 AEs that do not recover to Grade 1 or less within 12 weeks.
- Hepatic:

Proprietary confidential information © 2021 Boehringer Ingelheim International GmbH or one or more of its affiliated companies

- For Grade 2 events, monitor liver function tests more frequently until returned to baseline values (consider weekly).
 - Treat with i.v. or oral corticosteroids
- For Grade 3-4 events, treat with i.v. corticosteroids for 24 to 48 hours.
- When symptoms improve to Grade 1 or less, a steroid taper should be started and continued over no less than 28 days.
- BI 754091 and BI 754111 should be permanently discontinued for any recurrent Grade 3-4 AE, transaminase increases >5 times ULN or total bilirubin >3 times ULN (unless unequivocally attributable to another cause), inability to taper steroids to 10 mg or less prednisone or equivalent within 12 weeks, or persistent Grade 2-3 AEs that do not recover to Grade 1 or less within 12 weeks.
- Renal failure or nephritis:
 - For Grade 2 events, treat with corticosteroids.
 - For Grade 3-4 events, treat with systemic corticosteroids.
 - When symptoms improve to Grade 1 or less, steroid taper should be started and continued over no less than 28 days.
 - BI 754091 and BI 754111 should be permanently discontinued for any recurrent Grade 3-4 AE, inability to taper steroids to 10 mg or less prednisone or equivalent within 12 weeks, or persistent Grade 2-3 AEs that do not recover to Grade 1 or less within 12 weeks.
- Adrenal insufficiency:
 - BI 754091 and BI 754111 should be permanently discontinued for Grade 3-4 adrenal insufficiency or persistent Grade 2 AEs that do not recover to Grade 1 or less within 12 weeks.
- Rash:
 - BI 754091 and BI 754111 should be permanently discontinued for Grade 4 rash, any recurrent Grade 3 AE or persistent Grade 2-3 AEs that do not recover to Grade 1 or less within 12 weeks.
- Encephalitis:
 - BI 754091 and BI 754111 should be permanently discontinued for any grade encephalitis.
- Infusion reactions:
Signs and symptoms usually develop during or shortly after drug infusion and generally resolve completely within 24 hours of completion of infusion.

10.3 **HANDLING PROCEDURES FOR BLOOD SAMPLES FOR PLASMA CONCENTRATION-TIME MEASUREMENTS**

Handling procedures for blood samples are presented in the Laboratory Manual.

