1.4 BENEFIT - RISK ASSESSMENT

The role of the immune-checkpoint inhibitors within a normal immune response is to dampen the immune response after the trigger (antigen) is resolved, minimizing collateral-immune-mediated damage to healthy tissue. Immune-checkpoint inhibitors also play a major role in promoting and maintaining self-tolerance by inactivating auto-reactive T-cells. Therefore, manipulation of immune-checkpoint-inhibitor pathways unleashes the immune system and comes with a higher risk of inducing immune dysfunction leading to immune-related adverse events (irAEs). Indeed, mice deficient in PD-1 or its ligands (PD-L1 and PD-L2) were found to be highly prone to development of autoimmune diseases ([R16-2362](#); [R16-2364](#); [R16-2968](#); [R16-2969](#); [R16-2970](#)).

Data from immune-checkpoint clinical trials show that irAEs occur frequently in patients treated with anti-CTLA-4 (90%) and anti-PD-1 or anti-PD-L1 (70%) mAbs. However, the majority of these AEs are mild in severity ([R12-5176](#); [R15-3588](#); [R15-3715](#)) and commonly occur within the first 4 months of initiating therapy ([R15-3780](#); [R16-0864](#); [R16-0899](#)). Immune-related AEs affect mainly the gastrointestinal tract (including diarrhoea and, less frequently colitis), skin (including rash/erythema and less frequently vitiligo), endocrine glands (including hypothyroidism, hyperthyroidism, and hypophysitis), liver (frequently asymptomatic elevated transaminases), and lung (pneumonitis), but could also potentially affect other tissues. Rare fatal cases of colitis, pneumonitis and myocarditis have been reported with use of immune-checkpoint inhibitors. The main treatment of irAEs is the administration of steroids for 2 to 4 weeks; other immunosuppressive agents (such as infliximab, mycophenolate mofetil and cyclosporine) can be used in case of steroid-refractory irAE ([R16-0763](#); [R16-0899](#)).

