5.2.7.5 Adverse events of special interest (AESIs)

The term AESI relates to any specific AE that has been identified at the project level as being of particular concern for prospective safety monitoring and safety assessment within this trial, e.g. the potential for AEs based on knowledge from other compounds in the same class. AESIs need to be reported to the sponsor’s Pharmacovigilance Department within the same timeframe that applies to SAEs as described in Section [5.2.7.8](#), subsections “AE Collection” and **AE reporting to sponsor and timelines**.

In this trial, DLTs, irAEs as defined in Appendix [10.1](#), infusion-related AEs, potential DILI events, and hepatic injury are AESIs.

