10. APPENDICES

10.1 IMMUNE-RELATED ADVERSE EVENTS OF SPECIAL INTEREST

Table 10.1: 1 Immune-related adverse events of special interest

This table defines immune-related AEs that must be reported as AESIs.

Immune-related adverse events of special interest
Pneumonitis (report as AESI if an irAE is \geq Grade 2) 
• Acute interstitial pneumonitis• Interstitial lung disease• Pneumonitis
Colitis (report as AESI if an irAE is \geq Grade 2 or any grade resulting in dose modification or use of systemic steroids to treat the AE) 
• Intestinal obstruction• Colitis• Colitis microscopic• Enterocolitis• Enterocolitis haemorrhagic• Gastrointestinal perforation• Necrotizing colitis• Diarrhea
Endocrine (report as AESI if an irAE is \geq Grade 3 or \geq Grade 2 and resulting in dose modification or use of systemic steroids to treat the AE) 
• Adrenal insufficiency• Hyperthyroidism• Hypophysitis• Hypopituitarism• Hypothyroidism• Thyroid disorder• Thyroiditis• Hyperglycaemia, if \geq Grade 3 and associated with ketosis or metabolic acidosis
Endocrine (report as AESI for any grade) 
• Type 1 diabetes mellitus (if new onset)

Immune-related adverse events of special interest

Hematologic (report as AESI if an irAE is \geq Grade 3 or any grade resulting in dose modification or use of systemic steroids to treat the AE)

- Autoimmune haemolytic anaemia
- Aplastic anaemia
- Thrombotic thrombocytopenic purpura
- Idiopathic (or immune) thrombocytopenia purpura
- Disseminated intravascular coagulation
- Haemolytic-uraemic syndrome
- Any Grade 4 anaemia regardless of underlying mechanism

Hepatic (report as AESI if an irAE is \geq Grade 2, or any grade resulting in dose modification or use of systemic steroids to treat the AE)

- Hepatitis
- Autoimmune hepatitis
- Transaminase elevations (ALT and/or AST)

Infusion Reactions (report as AESI for any grade)

- Allergic reaction
- Anaphylaxis
- Cytokine release syndrome
- Serum sickness
- Infusion reactions
- Infusion-like reactions

Neurologic (report as AESI for any grade)

- Autoimmune neuropathy
- Guillain-Barre syndrome
- Demyelinating polyneuropathy
- Myasthenic syndrome

Ocular (report as AESI if an irAE is \geq Grade 2 or any grade resulting in dose modification or use of systemic steroids to treat the AE)

- Uveitis
- Iritis

Immune-related adverse events of special interest

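### Appendix 10.2 gives Grade 3–4 diarrhoea not identified as colitis a later written steroid trigger (more than 1 week) than Grade 2 diarrhoea/colitis (more than 3 days)

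*Protocol*

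**What the plan says.** The Diarrhoea/Colitis part of Protocol Appendix 10.2 has three steroid instructions and one on work-up:

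- Grade 2: "For Grade 2 diarrhoea/colitis that persists greater than 3 days, administer oral corticosteroids".
- Grade 3–4 diarrhoea: "For Grade 3 or 4 diarrhoea that persists >1 week, treat with i.v. steroids followed by high-dose oral steroids".
- Grade 3–4 colitis, or recurrent colitis of any grade: "permanently discontinue BI 754091 and BI 754111, and immediately treat with i.v. steroids followed by high-dose oral steroids".
- Work-up: "For Grade 2 or higher diarrhoea, consider GI consultation and endoscopy to confirm or rule out colitis".

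Other provisions bear on how this guidance would be used:

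- Section 4.1.4 refers to Appendix 10.2 as guidelines. It also requires permanent discontinuation for drug-related events of Grade 4 or higher.
- Section 4.2.2.2 accepts immunosuppressive medication for managing product-related adverse events. Section 4.2.2.1 leaves supportive care to the investigator's discretion.
- Table 10.1: 1 lists diarrhoea under its Colitis entry, to be reported as an AESI when it is immune-related and of Grade 2 or higher. Section 5.2.7.5 requires AESIs to be reported "within the same timeframe that applies to SAEs as described in Section" 5.2.7.8, which is 24 hours.

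**The concern.** One would expect steroids to start sooner as severity rises, or at least no later. For diarrhoea the written order is the reverse: a site following the appendix literally would start steroids after day 3 at Grade 2, and would wait until after day 7 at Grade 3 or 4 if colitis had not been identified.

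What is at stake is treatment delay in a severe immune-related event. Section 1.4 places the gut among the main sites: "Immune-related AEs affect mainly the gastrointestinal tract (including diarrhoea and, less frequently colitis". It calls steroids the main treatment for these events and adds: "Rare fatal cases of colitis, pneumonitis and myocarditis have been reported with use of immune-checkpoint inhibitors". Appendix 10.2 itself names diarrhoea as a sign of enterocolitis to watch for. The later trigger therefore governs while colitis may be present but is not yet established.

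**Working it through.** The plan gives no calculated figure here, so the check compares the written rules.

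**Inputs** (Appendix 10.2, Diarrhoea/Colitis): the Grade 2 trigger is more than 3 days. The Grade 3–4 diarrhoea trigger is more than 1 week, that is, more than 7 days. Grade 3–4 colitis has no waiting time.

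**Difference:** 7 − 3 = 4 days, with the longer wait at the higher grade.

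**Steroid instruction by course and duration.** For a patient who presents at the stated grade, duration runs from onset. The appendix does not say how to count when the grade changes.

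| Duration of diarrhoea | Grade 2 throughout | Reaches Grade 3–4 before the Grade 2 trigger; colitis not identified | Grade 2 for more than 3 days, then Grade 3–4; colitis not identified | Grade 3–4 with colitis identified |
|---|---|---|---|---|
| Up to 3 days | none | none | none (still Grade 2) | intravenous, immediately |
| More than 3, up to 7 days | oral | **none** | oral already instructed | intravenous, immediately |
| More than 7 days | oral | intravenous, then high-dose oral | oral already instructed; intravenous once the Grade 3–4 trigger is met | intravenous, immediately |

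The gap is the single cell in bold.

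**Could another passage fill that cell?**

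- The 3-day bullet is worded for Grade 2 only, not Grade 2 or higher, so it is not a written first step for someone who presents at Grade 3.
- Table 10.1: 1 groups diarrhoea with colitis, but its stated purpose is reporting: "This table defines immune-related AEs that must be reported as AESIs". Appendix 10.2 has separate Grade 3–4 bullets for diarrhoea and colitis, so the immediate-treatment bullet cannot be read across.
- The 24-hour AESI report falls before both triggers and changes neither. The Grade 4 discontinuation rule stops study drug, sets no steroid start, and does not reach Grade 3.
- Sections 4.2.2.1 and 4.2.2.2 allow earlier treatment but set no time for it.

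**Rest of Appendix 10.2.** Where other organ sections instruct steroids at higher grades, none imposes a wait: pneumonitis Grade 3–4 (immediate), hypophysitis Grade 3 and Grade 4, hyperthyroidism Grade 3–4, hepatic Grade 3–4, renal Grade 3–4. Diarrhoea is the only entry where the higher grade waits longer, and no reason is given.

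**The case against.** The strongest reply is that the bullet says when steroids must be given and does not forbid them sooner. The appendix is guidance, and immunosuppression for product-related events is accepted at any time. Close monitoring for enterocolitis is required, and endoscopy is to be considered from Grade 2. Section 8.7 describes the target investigators as experienced in immune-oncology trials. Section 4.1.5 also takes it as normal that a Grade 3 immune-related event is treated with immunosuppression. A delay would occur only if a site read the threshold as a minimum wait. The Grade 3–4 regimen is also the stronger one once it starts. All of this stands and lowers the practical risk. None of it supplies the missing instruction, and permission to act earlier does not correct a stated trigger that runs the wrong way.

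Two stronger readings are tempting and not supported:

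- A reader might infer from Section 1.4 that the late trigger falls on the more common presentation. That section ranks diarrhoea above colitis among immune-related events of all grades, and says that most such events are mild. It gives no frequency for Grade 3–4 diarrhoea without identified colitis.
- A reader might infer that every patient with Grade 3–4 diarrhoea goes without a steroid instruction from day 3 to day 7. A patient who had Grade 2 diarrhoea for more than 3 days before worsening already has the oral instruction, so the intravenous bullet is then an escalation.

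**Conclusion.** The inconsistency is real and in the current text. The written trigger is 4 days later for Grade 3–4 diarrhoea not identified as colitis than for Grade 2 diarrhoea/colitis. Its consequence is confined to patients who reach Grade 3–4 without first meeting the Grade 2 trigger, in the band from more than 3 up to 7 days. How many patients that is, or whether any would in practice be treated late, cannot be told from the documents.

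The conclusion assumes only that the bullets mean what they say by grade. It does not assume a drafting error: a reader might take the one-week interval for a slip, but the documents do not show whether it was a slip or a deliberate distinction between diarrhoea and colitis. A reader might also infer a bias in DLT counts, because Section 4.1.5 exempts a Grade 3 immune-related event that resolves with immunosuppression within 2 weeks. Nothing in the documents shows that any DLT classification turned on this bullet, and no effect on dose finding or analysis is claimed.

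This is a patient-safety correction that should be made because it is specific and cheap. It does not call the design into question.

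**What to change.** Amend the Grade 3–4 diarrhoea bullet in Appendix 10.2 so that intravenous steroids, followed by high-dose oral steroids, start no later than the Grade 2 trigger: at the latest once diarrhoea has lasted more than 3 days. If the medical team prefers, make the start immediate, as already written for Grade 3–4 colitis. The choice between the two is clinical, and either removes the inversion. Tell sites of the change.

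The cost is one bullet in a protocol amendment and a site notice. Design, sample size, data collection and the SAP are unaffected.

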10.4 TIME SCHEDULE FOR PHARMACOKINETIC (PK), ADA, AND BIOMARKER BLOOD SAMPLING

Table 10.4: 1

Time schedule for PK, ADA, and biomarker blood sampling during treatment (Parts I and II)

Treatment Cycle	Visit	Day	CRF Time /PTM	Event	PK	ADA	PBMC ²⁾ (frozen)
1, 2, 4	1	1	-0:05 (Just before drug admin)	Blood	X	X	X (C1&2)
			0:00	Drug admin			
			1:00 (Immediately before end of infusion)	Blood	X		
			1:30	Blood	X		
			2:00	Blood	X		
			4:00	Blood	X		
			7:00	Blood	X		
	2	2	24:00	Blood	X		X (C1)
	3	3	48:00	Blood	X		
	4	4	72:00	Blood	X		
	5	8 ±1	168:00	Blood	X		X (C1)
	6	15±1	336:00	Blood	X		
3, 5-12, 14, 17 ¹⁾	1	1	-0:05 (Just before drug admin)	Blood	X	X	X (C3&5)
			0:00	Drug admin			
EOT				Blood	X	X	
FU				Blood	X	X	X

1) every 3 cycles after Cycle 17

2) PBMC sample will be taken in Part II (only if feasible)

Table 10.4: 2 Time schedule for PK, ADA, and biomarker blood sampling during treatment (Part III)

Treatment Cycle	Visit	Day	CRF Time /PTM[hh:mi:n]	Event	PK	ADA	PBMC (extract)	PBMC (blood)	Cytokine
1, 4	1	1	-0:05 (Just before drug admin)	Blood	X	X	X (C1)	X (C1)	X
			0:00	Drug admin					
			1:00 (Immediately before end of infusion)	Blood	X				
	2	2	24:00	Blood	X		X (C1)		X
	3	8 ±1	168:00	Blood	X		X (C1)	X (C1)	X
	4	15±1	336:00	Blood	X			X (C1)	
2, 3, 5-12, 14, 17 ¹⁾	1	1	-0:05 (Just before drug admin)	Blood	X	X	X (C2, 3, and 5)	X (C2)	X (C2, C3)
			0:00	Drug admin					
EOT ²⁾				Blood	X	X		X	
FU ²⁾				Blood	X	X	X		X

1) every 3 cycles after Cycle 17

2) blood samples for PK, ADA, PBMC and cytokines are not required after the interim database lock

10.5 STATISTICAL APPENDIX INCLUDING MODEL PERFORMANCE AND DATA SCENARIOS

A Bayesian logistic regression model with overdose control will be used to guide dose-finding in this study. The BLRM is introduced in Section 7.1, which also specifies the prior for the model. After patients in each cohort have completed at least one cycle of treatment, the prior distribution will be updated through Gibbs sampling procedures with the accumulated DLT data from the MTD evaluation period. Posterior probabilities for the rate of DLTs will be summarised from BLRM. Selection of the next dose will be based on these probabilities as well as on other safety and laboratory data.

The purpose of this statistical appendix is to present performance metrics (operating characteristics) that illustrate the precision of the design in estimating the MTD under various dose-toxicity relationships through computer simulation. These results are summarized in [Table 10.5: 3](#). In addition, recommendations of the next dose level by the BLRM with overdose control principle are also provided under various hypothetical outcome scenarios in early cohorts to show how it facilitates on-study dose-finding decisions (see [Table 10.5: 1](#)). At 1st SMC, 6 patients will be evaluated in part 1. After that, a cohort size of 3 patients who are all evaluable is assumed. Though the simulation results are showed, the next dose level decision will be done by the SMC. The simulations for scenarios and operating characteristics were produced using RStudio version 3.3.2 in conjunction with WinBUGS 1.4.3.

Hypothetical data scenarios

Hypothetical data scenarios are shown in [Table 10.5: 1](#). These scenarios reflect potential on-study data constellations and related escalation as allowed by the model. For each scenario, the probability of overdose for the current dose, as well as the next potential dose and related probabilities of under-dosing, target dose, and over-dosing are shown.

For example, scenario 1 represents the case that no DLT is observed in the first 6 patients at the starting dose of 240 mg. In this case, the next dose recommended by BLRM is 240 mg. And the SMC may conclude the completion of part 1.

Scenario 2 and 3 represents that the case that 1 or 2 DLTs are observed in the first 6 patients at the starting dose of 240 mg. In this case, the next dose level recommended by BLRM is 240 mg.

Scenario 4 and 5 represents that the case that 1 DLT is observed in the first 6 patients at the starting dose of 240 mg, and the next dose level is kept the same where 0 or 1 DLT occurred.

Scenario 6 and 7 represents that the case that 2 DLTs are observed in the first 6 patients at the starting dose of 240 mg and the next dose level is different based on the SMC decision.

Table 10.5: 1 Hypothetical data scenarios

Scenario	Dose (mg)	# Patients	# DLT	Current Dose : P(OD)	Next recommended dose (mg)	Next dose:		
						P(UD)	P(TD)	P(OD)
1	240	6	0	0.005	240	0.926	0.069	0.005
2	240	6	1	0.043	240	0.686	0.271	0.043
3	240	6	2	0.173	240	0.367	0.460	0.173
4	240	6	1					
	240	3	0	0.015	240	0.795	0.195	0.015
5	240	6	1					
	240	3	1	0.071	240	0.519	0.410	0.071
6	240	6	2					
	80	3	0	0.010	240	0.452	0.435	0.112
7	240	6	2					
	240	3	1	0.207	240	0.255	0.537	0.207

Operating characteristics

Operating characteristics are a way to assess the long-run behaviour of a model by illustrating the precision of the design in estimating the MTD. Under an assumed true dose-toxicity curve, metrics such as the probability of recommending a dose with true DLT rate in the target interval can be approximated via simulation. Table 10.5: 2 describes 4 assumed true dose-toxicity scenarios which were used to assess the operating characteristics of the model. The scenario setting was referred to 1381-0001 trial assumptions. These scenarios reflect a wide range of possible cases as follows:

- Scenario 1: aligned with prior means
- Scenario 2: low-toxicity scenario
- Scenario 3: high-toxicity scenario
- Scenario 4: low-toxicity followed by high-toxicity

Table 10.5: 2 Assumed true dose-toxicity scenarios

Scenario		Dose (mg)		
		80	240	400
1: Prior	P(DLT)	0.096	0.164	0.257
2: Low Tox		0.001	0.009	0.028
3: High Tox		0.100	0.200	0.300

4: Low-High		0.001	0.180	0.360
-------------	--	-------	-------	-------

For each of these scenarios, 1000 trials were simulated. The each cohort consisted of 3 patients and the MTD was considered reached if at least 6 patients have been evaluated at a dose level which is the model's recommendation for the next dose cohort and for which the posterior probability of targeted toxicity was at least 50%.

It was then assessed how often a dose was declared as MTD with true DLT rate in the under-, targeted-, or over-dose range. Furthermore, the average, minimum and maximum number of patients per trial and the average number of DLTs per trial are reported. Results are shown in Table 10.5: 3.

Table 10.5: 3 Simulated operating characteristics

Scenario	% of trials declaring a MTD with true DLT rate in				# Patients	# DLTs
	Underdose	Target dose	Overdose	Stopped Before MTD		
1: Prior	44.2	53.4	0	2.4	10.1 (3-33)	1.59 (1-6)
2: Low Tox	76.9	0	0	23.1	34.8 (6-60)	0.8 (0-2)
3: High Tox	50.7	45.5	0	3.8	9.56 (3-33)	1.67 (1-6)
4: Low-High	48.9	42.3	8.0	0.8	9.78 (3-30)	1.39 (1-6)

In scenario 1 (Prior), which reflects the case that the true dose-toxicity is aligned with prior means, 53.4% of the simulated trials that have found a MTD declared the MTD with true toxicity rate in the target interval. Few simulated trials (2.4%) have been stopped before declaring a MTD.

In scenario 2 (Low-toxicity scenario), since none of the assumed true dose-toxicity scenarios were beyond 16%, 76.9% of the simulated trials declared a dose as MTD with true DLT rate in the under dose range. 23.1% of the trials stopped before MTD was reached.

In scenario 3 (High-toxicity scenario) illustrate a behaviour similar to scenario 1 because of the similar setting dose toxicity scenarios.

In scenario 4 (Low-High scenario) shows 42.3% of the simulated trials declared a dose as MTD with true DLT rate in the targeted dose range. 8.0% of the simulated trials declared a dose as MTD in the overdose range. This is because the assumed true dose-toxicity rate at 400 mg was above 33%.

The mean patients numbers range from 9 to 10 patients except for scenario 2 (Low-toxicity scenario). The mean patients number was around 35 patients at scenario 2. But in case low toxicity and no safety concern at RD level (i.e. 240 mg), the SMC may recommend stopping the dose finding phase.

In summary, the considered data scenarios show a reasonable behaviour of the model and the operating characteristics demonstrate a good precision of MTD determination.

Part II

The purpose of this statistical appendix is to present performance metrics (operating characteristics) that illustrate the precision of the design in estimating the MTD under various dose-toxicity relationships through computer simulation. These results are summarized in [Table 10.5: 6](#). In addition, recommendations of the next dose level by the BLRM with overdose control principle are also provided under various hypothetical outcome scenarios in early cohorts to show how it facilitates on-study dose-finding decisions (see [Table 10.5: 4](#)).

Hypothetical data scenarios

Hypothetical data scenarios are shown in [Table 10.5: 4](#). These scenarios reflect potential on-study data constellations and related escalation as allowed by the model. For each scenario, the probability of overdose for the current dose, as well as the next potential dose and related probabilities of under-dosing, target dose, and over-dosing are shown.

For example, scenario 1 represents the case that no DLT is observed in the first 3 patients at the starting dose of 240/400 mg. In this case, the next dose recommended by BLRM is 240/600 mg.

Scenario 2 represents that the case that 1 DLT is observed in the first 3 patients at the starting dose of 240/400 mg. In this case, the next dose level is 240/400 mg.

Scenario 3 represents that the case that 1 DLT is observed in the first 3 patients at the starting dose of 240/400 mg. And no DLTs is observed at next dose level 240/400 mg. In this case, the next dose level is 240/600 mg.

Scenario 4 represents that the case that 1 DLT is observed in the first 3 patients at the starting dose of 240/400 mg. And 1 DLT is observed at next dose level 240/400 mg. In this case, the next dose level is 240/200 mg.

Scenario 5 represents the case that no DLT is observed in the first 3 patients and next 3 patients. In this case, the next dose recommended by BLRM is 240/800 mg.

Table 10.5: 4 Hypothetical data scenarios

Scenario	Dose comb. BI754091/ BI754111 (mg/mg)	# Patients	# DLT	Current Dose : P(OD)	Next dose comb. BI754091/ BI754111 (mg/mg)	Next dose:		
						P(UD)	P(TD)	P(OD)
1	240/400	3	0	0.024	240/600	0.874	0.077	0.048
2	240/400	3	1	0.279	240/200	0.562	0.251	0.186
3	240/400	3	1					
	240/400	3	0	0.084	240/600	0.631	0.203	0.166
4	240/400	3	1					
	240/400	3	1	0.333	240/200	0.214	0.219	0.163
5	240/400	3	0					
	240/600	3	0	0.008	240/800	0.934	0.044	0.022

Operating characteristics

Operating characteristics are a way to assess the long-run behaviour of a model by illustrating the precision of the design in estimating the MTD. Under an assumed true dose-toxicity curve, metrics such as the probability of recommending a dose with true DLT rate in the target interval can be approximated via simulation. Table 10.5: 5 describes 4 assumed true dose-toxicity scenarios which were used to assess the operating characteristics of the model. These scenarios reflect a wide range of possible cases as follows:

- Scenario 1: aligned with prior means
- Scenario 2: low-toxicity scenario
- Scenario 3: high-toxicity scenario
- Scenario 4: low-toxicity followed by high-toxicity

Table 10.5: 5 Assumed true dose-toxicity scenarios

Scenario		BI 754091 / BI 754111 (mg / mg)			
		240 / 200	240 / 400	240 / 600	240 / 800
1: Prior	P(DLT)	0.146	0.175	0.198	0.214
2: Low Tox		0.001	0.009	0.028	0.160
3: High Tox		0.100	0.200	0.300	0.600
4: Low-High		0.001	0.180	0.360	0.720

Proprietary confidential information © 2021 Boehringer Ingelheim International GmbH or one or more of its affiliated companies

For each of these scenarios, 1000 trials were simulated. The each cohort consisted of 3 patients and the MTD was considered reached if at least 6 patients have been evaluated at a dose level which is the model's recommendation for the next dose cohort and for which the posterior probability of targeted toxicity was at least 50%.

It was then assessed how often a dose was declared as MTD with true DLT rate in the under-, targeted-, or over-dose range. Furthermore, the average, minimum and maximum number of patients per trial and the average number of DLTs per trial are reported. Results are shown in Table 10.5: 6.

Table 10.5: 6 Simulated operating characteristics

Scenario	% of trials declaring a MTD with true DLT rate in				# Patients	# DLTs
	Underdose	Target dose	Overdose	Stopped Before MTD	Mean (Min-Max)	Mean (Min-Max)
1: Prior	14.0	69.3	0	16.7	27.41 (9-60)	1.24 (0-4)
2: Low Tox	21.0	72.8	0	6.2	11.97 (3-42)	2.161 (1-7)
3: High Tox	8.6	75.4	1.5	14.5	11.5 (3-30)	2.5 (1-9)
4: Low-High	5.5	66.9	18.2	9.4	11.7 (3-42)	2.57 (1-9)

In scenario 1 (Prior), which reflects the case that the true dose-toxicity is aligned with prior means, 69.3% of the simulated trials that have found a MTD declared the MTD with true toxicity rate in the target interval.

In scenario 2 (Low-toxicity scenario), almost all simulated trials (93.8%) are declared as MTD in underdose or target dose. The result is similar to scenario 1.

In scenario 3 (High-toxicity scenario), 75.4 % of the simulated trials are declared to MTD with true toxicity rate in the target intervals. Though overdose toxicity is assumed but the only 1.5% is declared as MTD in overdose.

In scenario 4 (Low-High scenario) shows 66.9% of the simulated trials declared a dose as MTD with true DLT rate in the targeted dose range. 18.2% of the simulated trials declared a dose as MTD in the overdose range. This is because the assumed true dose-toxicity rate at 240/600 mg and 240/800 mg was above 33%.

The mean patients numbers range is from 3 to 60 patients and the DLT numbers range is from 0 to 9.

In summary, the considered data scenarios show a reasonable behaviour of the model and the operating characteristics demonstrate a good precision of MTD determination.

10.6 iRECIST

Immunotherapeutics may result in infiltration of immune cells leading to transient increase in the size in malignant lesions, or undetectable lesions becoming detectable. The criteria are identical to those of RECIST 1.1 in many respects but have been adapted to account for instances where an increase in tumour burden, or the appearance of new lesions, does not reflect true tumour progression. Key differences are described below. All responses defined using iRECIST criteria are designated with a prefix. iRECIST time-point and best overall responses will be recorded separately.

Confirming progression

Unlike RECIST 1.1, iRECIST requires the confirmation of progression and uses the terms iUPD (unconfirmed progression) and iCPD (confirmed progression). Confirmatory scans should be performed at least 4 weeks, but no longer than 8 weeks after iUPD.

iCPD is confirmed if further increase in tumour burden, compared to the last assessment, is seen as evidenced by one or more of the following:

- Continued increase in tumour burden (from iUPD) where RECIST 1.1 definitions of progression had been met (from nadir) in target, non-target disease or new lesions
 - Progression in target disease worsens with an increase of at least 5 mm in the absolute value of the sum
 - Continued unequivocal progression in non-target disease with an increase in tumour burden
 - Increase in size of previously identified new lesion(s) (an increase of at least 5 mm in the absolute value of the sum of those considered to be target new lesions) or additional new lesions
- RECIST 1.1 criteria are met in lesions types (target or non-target or new lesions) where progression was not previously identified, including the appearance of additional new lesions.

If iUPD is not confirmed at the next assessment, then the appropriate response will be assigned (iUPD if the criteria are still met, but no worsening, or iSD, iPR or iCR if those criteria are met compared to baseline). The prior documentation of iUPD does not preclude assigning iCR, iPR, or iSD in subsequent time-point assessments or as best overall response (BOR) providing that iCPD is not documented at the next assessment after iUPD.

New lesions

New lesions should be assessed and measured as they appear using RECIST 1.1 criteria (maximum of 5 lesions, no more than 2 per site, at least 10 mm in long axis (or 15 mm in short axis for nodal lesions), and recorded as New Lesions-Target (NLT) and New

Proprietary confidential information © 2021 Boehringer Ingelheim International GmbH or one or more of its affiliated companies

Lesion-Non-Target (NLNT) to allow clear differentiation from baseline target and non-target lesions.

New lesions may either meet the criteria of NLT or NLNT to drive iUPD (or iCPD). However, the measurements of target lesions should NOT be included in the sum of measures of original target lesions identified at baseline. Rather, these measurements will be collected on a separate table in the case record form.

PD is confirmed in the New Lesion category if the next imaging assessment, conducted at least 4 weeks (but not more than 8 weeks) after iUPD confirms further progression from iUPD with either an increase of at least 5 mm in the absolute value of the sum of NLT OR an increase (but not necessarily unequivocal increase) in the size of NLNT lesions OR the appearance of additional new lesions

Table 10.6: 1 Time-point (TP) iResponse

Target Lesions*	Non-Target Lesions*	New Lesions *	Time Point Response	
			No prior iUPD**	Prior iUPD**; ***
iCR	iCR	No	iCR	iCR
iCR	Non-iCR/Non-iU PD	No	iPR	iPR
iPR	Non-iCR/Non-iU PD	No	iPR	iPR
iSD	Non-iCR/Non-iU PD	No	iSD	iSD
